8.10 Subject Withdrawal

Subjects have the right to withdraw their consent at any time during the study. If a subject requests to withdraw from the study, all information regarding the subject's withdrawal and disposition must be recorded in the subject's medical record. A Study Exit case report form, including a full description of the circumstances related to the withdrawal, must be completed.

8.11 Study Case Report Forms

The Sponsor will provide Case Report Forms (CRFs) to the sites for the study on paper and electronically, when available. Data should be entered on the paper CRFs with black ink. If an error is made on a CRF, the incorrect entry should be crossed out with a single horizontal line, the correct entry written next to it, and the correction initialed and dated by the person making the correction. Copies of the CRFs for the study are included as an appendix to the protocol.

8.11.1 List of Case Report Forms

- Inclusion/Exclusion
- Pre-Operative
- Operative/Discharge
- Follow-Up Visit which includes:
 - Initial Post-Op Follow-Up Visit (between 2-8 weeks post-op)
 - 3 Month Follow-Up Visit \pm 2 Weeks
 - 6 Month Follow-Up Visit \pm 1 Month
 - 12 Month Follow-Up Visit \pm 2 Months
 - 24 Month Follow-Up Visit \pm 2 Months
 - Unscheduled Visit
 - Odom's Criteria (24 Month Visit Only)
- Patient Questionnaires:
 - Back Visual Analog Scale (VAS) and Leg Visual Analog Scale (VAS)
 - SRS-22r
 - Patient Satisfaction
- Adverse Event
- Protocol Deviation
- Study Exit

9 ADVERSE EVENTS

9.1 Definitions

9.1.1 Adverse Event

An Adverse Event (AE) is defined as any untoward medical occurrence in a subject undergoing surgery in this trial which does not necessarily have a causal relationship with this intervention. An AE can, therefore, be any unfavorable and unintended sign (including an abnormal laboratory finding), symptom, or disease temporally associated with the use of one of the devices, whether or not the event is considered causally related to the use of the device. Any worsening of a pre-existing condition or illness is considered an AE. Laboratory abnormalities and changes in vital signs are considered to be AEs only if they result in discontinuation from the study, necessitate therapeutic medical intervention that could impact the study surgical outcomes, and/or if the Investigator considers them to be AEs.

9.1.2 Serious Adverse Event

Any AE that results in one or more of the following is considered a Serious Adverse Event (SAE): death, life threatening situation, inpatient hospitalization, persistent or significant disability/incapacity, and other medically important events. Definitions of SAEs are:

Death: the subject dies during participation in the study.

Life threatening situation: the subject is at risk of death at the time of the event, but does not refer to the hypothetical risk of death if the AE were more severe or were to progress.

Inpatient hospitalization: a subject requires hospitalization or prolongation of an existing hospitalization, including medical or surgical intervention to prevent permanent impairment to a body structure or body function during participation in a clinical study.

Persistent or significant disability/incapacity: any AE having an outcome that is associated with a substantial disruption of the ability to carry out normal life functions. This includes the inability to work or attend school, but is not intended to include transient interruptions of daily activities.

Other medically important events: important medical events that may not result in death, be life-threatening, or require hospitalization (including emergency room visits) but may be considered a serious AE when, based upon medical judgment, they may jeopardize the subject.

Reports of all Serious Adverse Events, as classified by the Investigator, will be reviewed on a periodic basis by the Medical Monitor.

9.1.3 Subsequent Surgical Interventions

The cause for subsequent surgical interventions should be listed as a serious adverse event.

Subsequent surgical interventions are classified as follows:

Revision: a procedure that adjusts or in any way modifies the original implant configuration. A revision may also include adjusting the position of the original configuration.

Removal: a procedure where all of the original system configuration are removed with or without replacement.

Supplemental Fixation: a procedure in which additional instrumentation not under study in the protocol is implanted.

Re-Operation: any surgical procedure at the involved level that does not require removal, modification, or addition of any components to the system.

9.2 Adverse Event Reporting

Any AE that occurs during the subject's participation in the study will be recorded on the Adverse Event case report form. Pre-existing medical conditions or symptoms occurring prior to the initiation of the study will not be reported as AEs but a worsening of a pre-existing medical condition or symptom will be reported as an AE. Pain, neurological status and functional impairment should be considered AEs when a subject's complaint for any of these symptoms results in an unscheduled visit or when a subject presents with new or worsening symptoms as compared to a previous visit.

All AEs will be followed until the event is resolved or considered to be stable. Relevant source documentation must be available to confirm the occurrence of an AE and must be provided to the sponsor upon request.

9.2.1 Serious Adverse Event Reporting

Independent of the relationship to the study device or device procedure, the site must report SAEs to the Sponsor immediately upon becoming aware of the events and subsequently submit the appropriate CRFs within 10 working days. SAEs will be investigated and reported to the FDA if they fall within the appropriate guidelines for Medical Device Reporting (MDR). The site must also report SAEs to the reviewing Institutional Review Board (IRB)/Ethics Committee (EC) according to IRB/EC requirements.

The site must confirm the SAE in appropriate source documents and provide detailed information pertaining to the event to the sponsor and reviewing IRB/EC if requested.

9.3 Adverse Event Severity

The Investigator will be asked to characterize the severity of each AE as mild, moderate or severe. The assessment is subjective and the Investigator will use medical judgment to compare the reported AE to similar types of events observed in clinical practice. Guidelines for AE severity assessment are as follows:

Mild: The AE is transient and easily tolerated by the subject. No medical treatment required.

Moderate: The AE causes the subject discomfort and interrupts the subject's usual activities. Medical treatment required to alleviate or lessen the impact of this untoward condition.

Severe: The AE causes considerable interference with the subject's usual activities may be incapacitating and may require hospitalization. **See Section 9.1.3. Serious Adverse Events.**

9.4 Adverse Event Association

The relationship of all AEs to the device, the procedure or general surgery will be classified by the Investigator as not related, possibly related, probably related or definitely related.

Not related: The AE is due to an underlying or concurrent illness or effect of another device, drug or intervention and is not related to the study device, procedure or general surgery.

Possibly related: The causal and/or temporal relationship to the study device, procedure or general surgery, is equally or less likely than other plausible explanations.

Probably related: The causal and/or temporal relationship to the study device, procedure or general surgery, is likely or significantly more likely than other plausible explanations.

Definitely related: A clinical event that can only be attributed to the device, procedure or general surgery.

9.5 Potential Risks and Anticipated Adverse Events

9.5.1 General Surgery Risks

General surgical risks are but may not be limited to:

- Airway Obstruction
- Anaphylaxis
- Anesthesia Related
- Atelectasis
- Blood Clots, including Pulmonary Emboli
- Cardiac Arrest
- Cardiac, Other
- CVA
- Death
- Decompensation
- Deep Vein Thrombosis
- Epidural Fibrosis
- Epidural Hematoma or Bleeding
- Excessive Blood Loss
- Hemorrhage Possibly Requiring a Blood Transfusion
- Infection, Deep Wound
- Infection, Superficial Wound
- Infection, Urinary Tract
- Infection, Other
- Myocardial Infarction
- Phlebitis
- Pleural Effusion
- Pneumonia
- Pneumothorax
- Poor Tissue Healing
- Retained Sponge
- Septicemia
- Suture Abscess
- Transfusion Reaction
- Vascular or Blood Vessel Injury
- Wound Dehiscence

9.5.2 Posterior Fusion Surgery Risks

Posterior Fusion surgical risks are but may not be limited to:

- Allergic Reaction to the Implant/Retractor Materials
- Bowel or Bladder Dysfunction
- Disc Height Loss
- Dural Tear (with or without Cerebrospinal Fluid Leak)
- Dysesthesia or Numbness
- Erosion due to Implant
- Nerve Injury
- Nerve Root Injury
- Osteolysis
- Pain, New Onset
- Pain, Unresolved
- Paralysis
- Pseudoarthrosis
- Spinal Cord Damage
- Failure to Relieve Symptoms, including Unresolved Pain
- Foreign Body Reaction
- Kyphosis or Hyper-Extension
- Loss of Spinal Flexibility
- Muscle and Tissue Injury or Damage
- Sexual Dysfunction
- Spinal Degeneration
- Spinous Process Fracture
- Surgical Intervention at Incorrect Levels
- Tingling
- Thigh Pain
- Vertebral Body Fracture
- Weakness

9.5.3 K2M Device Risks

Risks specific to the MESA Rail Deformity System are but may not be limited to:

- Bone Graft Migration
- Bone Graft Subsidence
- Device Instability
- Device Malposition
- Device Migration
- Device Subsidence
- Disengagement – from Bone
- Disengagement – Screw/Rod Interface
- Foreign Body Reaction
- Hook/Rod Interface Disengagement
- Material Degradation
- Prominent Implants
- Rod Breakage
- Screw Breakage or Back-out
- Set Screw Loosening
- Screw/Rod Interface Slide

10 SITE REGULATORY REQUIREMENTS

10.1 Institutional Review Board (IRB)/Ethics Committee (EC) Approval

Prior to enrolling subjects in the study, site IRB/EC approval must be obtained and must be maintained by the site throughout the study. The IRB/EC approval letter(s) must be maintained in the study files at all times.

10.2 Study Specific Informed Consent

The informed consent process when executed properly provides sufficient information about study procedures so that a potential participant can voluntarily make a reasonable decision about participation, based on an understanding of the purpose, potential risks and anticipated benefits (if any) of the study. Informed consent is not a waiver of rights.

When individuals who do not have the authority to consent to participate in research, either because they are minors or because they are physically or mentally incapable of making informed decisions, they must still provide their assent or agreement to participate in a study from the individual. Assent is an active affirmation of a desire to participate and differs from consent which is recognized as being granted from an individual with the legal authority to do so. Even very young children or those with limited cognitive ability can assent and they can certainly indicate a desire not to participate, which must be honored. No individual should be enrolled in a study if they do not want to participate, even in cases where their legal guardian consents to their participation.

A study specific sample informed consent will be provided to each site prior to the IRB/EC process. The sample informed consent should be used as a template for creating the IRB/EC specific informed consent document as well as an abbreviated assent document (which should be no longer than a single page in length). Please refer to the IRB/EC that oversees research at your institution/site for rules and requirements related to informed consent and assent for the governing IRB/EC for your site.

Prior to submission of the proposed informed consent/assent documents to the reviewing IRB/EC, the Sponsor must review the informed consent/assent for completeness according to the protocol and according to 21 CFR Part 50 (US) and applicable international regulations. Potential study subjects should be offered informed consent according to the process outlined in **Section 8.1 Patient Screening and Enrollment**.

Patients must not be offered informed consent until written proof of IRB/EC approval is attained. The patient should be given the opportunity to take home a copy of the informed consent to review and discuss with family members or acquaintances prior to signing. Potential study subjects must also be given the opportunity to discuss the procedure, risks, benefits, alternative treatments and study requirements prior to signing the informed consent. They should be informed that they are free to refuse participation in this study and refusal will not affect their medical treatment. If patients elect to participate, it should be made clear that they may withdraw from the study for any reason and at any time without prejudicing further care.

A copy of the signed and dated IRB/EC approved Informed Consent and Assent Documents should be given to all subjects.

10.3 Regulatory Documents

Prior to patient enrollment, the following documents must be provided to the Sponsor and be on file at the site:

- Curriculum vitae and copy of medical license for Principal and Sub-Investigators
- IRB/EC approval letter and IRB/EC roster
- IRB/EC approved Informed Consent Form and Assent form, as required
- Signed Clinical Research Agreement
- Signed Investigators Agreement for Principal and Sub-Investigators, as required
- Finalized budget agreement
- Financial disclosures for the Principal and Sub-Investigators
- Site Initiation documentation

11 SITE VISIT/MONITORING PROCEDURES

Monitoring of the study will be a continuous process conducted in accordance with 21 CFR 812.46, applicable international regulatory requirements and Sponsor procedures. Monitoring will be performed by qualified clinical research personnel, or designees, of K2M.

11.1 Site Qualification Visit

Prior to selecting an Investigator for participation in the study a Qualification visit will be performed by K2M clinical staff or designee. The purpose of the visit is to confirm that the Investigator/investigative site has adequate staff, including a designated Study Coordinator, and facilities to perform the study according to the requirements of the protocol.

11.2 Study Initiation Visit

Prior to enrolling subjects at a study site, a Site Initiation Visit will be performed. The purpose of the visit is to confirm that the site continues to be qualified for participation and to review the Investigator/site responsibilities and requirements for the study. Site training will be performed and will include:

- Review of the clinical protocol and data collection process
- Monitoring requirements
- IRB/EC requirements
- Informed Consent process
- Review of site records

11.3 Periodic Monitoring Visits

Periodic site monitoring visits will be performed during the study by a designated study monitor assigned by the Sponsor. The purposes of the visits are to confirm compliance to the protocol, review regulatory documents, accurate and complete records are being maintained and to compare source documents to completed CRFs for completeness and consistency. The initial monitoring visit to a site will be scheduled soon after the first 2 to 5 patients are enrolled in the study and may occur prior to the first surgery. The frequency of subsequent visits will be dependent upon the rate of enrollment and site performance on previous monitoring visits. If possible, monitoring visits will be performed at least annually. Specific assessments during a monitoring visit include:

- Continued site acceptability
- Compliance to the protocol
- IRB/EC approval status
- Use of the approved informed consent
- Adequacy of source documents
- Complete and accurate CRFs
- Reporting of adverse events
- Protocol deviations
- Site records

If it is determined during a monitoring visit that there are significant non-compliance issues at a site, including adherence to the protocol or applicable regulatory requirements, the issues will be discussed with the Investigator and Study Coordinator and the site will be instructed how to gain compliance. If continued non-compliance is detected on a subsequent monitoring visit, it may be necessary to terminate site participation in the study.

11.4 Final Close-Out Visit

At the completion of the last long-term follow-up visit at each site a final close-out visit will be performed. The purpose of the visit will be to:

- Reconcile all outstanding data queries
- Review Site Records

- Review the records retention requirements for the study
- Arrange for the return of all study related materials to the Sponsor
- Review the final IRB/EC requirements for the study

12 STATISTICAL METHODS

12.1 Study Design

Prospective, non-randomized (single-arm) multi-center study to evaluate the effectiveness of the K2M MESA Rail compared to literature reported outcomes for standard Ø5.5mm or Ø4.5mm CoCr (as appropriate) rod systems for the treatment of AIS.

12.2 Study Hypothesis

The primary objective of this study is to evaluate the effectiveness of the MESA Rail Deformity System in terms of restoring and maintaining thoracic kyphosis in the treatment of patients with symptomatic AIS. The primary effectiveness endpoint is the rate of overall subject success (minimal loss of thoracic kyphosis) at 24 months. The primary hypothesis of this trial is that the clinical performance of the K2M MESA Rail implant is non-inferior to the clinical performance achieved and achieved with fusion utilizing a standard Ø5.5mm or Ø4.5mm CoCr rod.

A PubMed literature review was conducted to assemble relevant publications utilizing results from posterior instrumentation fusion surgeries in patients with AIS. Searches included all peer-reviewed journals published between January 2000 and March 2013. Sample sizes, patient populations, evaluated variables, results, and recorded complications were assessed for each selected article. Only data regarding thoracic kyphosis measurements of single-stage posterior fusion cases were incorporated into the thoracic kyphosis table used for statistical analysis. Articles were entirely excluded from the statistical analysis if results combined data from multi-stage cases or if data were extracted through meta-analysis.

The following table gives the preoperative thoracic kyphosis measurements as well as the thoracic kyphosis measurements collected at the last follow-up period from all relevant posterior fusion surgeries in patients with AIS:

| Thoracic Kyphosis | | | | | | | | | |
|----------------------------------|-----|-------|------|---------|------|------|------|---------------------|-------------|
| paper # | n | Preop | | Last FU | | Diff | | Mean difference x N | Std Dev x N |
| | | Mean | SD | Mean | SD | Mean | SD | | |
| 1 ¹ | 9 | 31.9 | 10.4 | 26.0 | 9.8 | 5.9 | 10.1 | 53.1 | 90.9 |
| 1 | 3 | 31.0 | 9.5 | 29.7 | 5.5 | 1.3 | 7.5 | 3.9 | 22.5 |
| 1 | 34 | 28.2 | 13.0 | 26.5 | 11.0 | 1.7 | 12.0 | 57.8 | 408.0 |
| 1 | 9 | 23.0 | 8.0 | 23.0 | 11.0 | 0.0 | 9.5 | 0.0 | 85.5 |
| 1 | 60 | 26.7 | 13.0 | 25.0 | 9.6 | 1.7 | 11.3 | 102.0 | 678.0 |
| 1 | 31 | 22.8 | 11.0 | 25.7 | 8.8 | -2.9 | 9.9 | -89.9 | 306.9 |
| 2 ² | 83 | 23.0 | 12.0 | 20.2 | 8.4 | 2.8 | 11.4 | 234.9 | 946.2 |
| 3 ³ | 111 | 29.0 | 14.0 | 23.0 | 10.8 | 6.0 | 12.2 | 666.0 | 1354.2 |
| 3 | 299 | 22.0 | 14.1 | 22.0 | 10.3 | 1.0 | 5.0 | 299.0 | 1495.0 |
| Weighted Mean Difference and SD: | | | | | | | | 2.1 | 8.4 |

The study hypothesis is that the RAIL system is superior to other systems in Thoracic Kyphosis Correction. The hypotheses can be written:

$$\begin{aligned} H_0: \mu_R &< OPC - \delta \\ H_1: \mu_R &\geq OPC - \delta \end{aligned}$$

where μ_R is the mean Thoracic Kyphosis Correction of the RAIL system and OPC is the Objective Performance Criteria of 2.2 and $\delta = 2$ degrees.

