12.3 Sample Size

If the mean Thoracic Kyphosis Correction of the RAIL system is 4.0 with a standard deviation of 8.4, then 173 subjects provides 80% power to detect a statistically significant difference between the mean correction and the OPC of 2.2 using a two-sided one-sample t-test at a significance level of 0.05. In order to account for approximately 15% attrition, based on clinical experience, 204 subjects will be enrolled.

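### The n=299 row, 47% of the literature benchmark's weight, is internally inconsistent, so the stated 80% power is unsupported until the row is traced to its source

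*Combined protocol and SAP*

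**What the plan says.** Section 12.2 (Study Hypothesis) tabulates nine literature groups with pre-op and last follow-up kyphosis, the mean and SD of the difference, and each of these multiplied by n. The last row is "299 | 22.0 | 14.1 | 22.0 | 10.3 | 1.0 | 5.0 | 299.0 | 1495.0". The other row from the same paper is "111 | 29.0 | 14.0 | 23.0 | 10.8 | 6.0 | 12.2 | 666.0 | 1354.2". The foot of the table gives "Weighted Mean Difference and SD: | | | | | | | | 2.1 | 8.4".

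The same section then states that "OPC is the Objective Performance Criteria of 2.2" degrees. Section 12.3 (Sample Size) takes over the SD: "If the mean Thoracic Kyphosis Correction of the RAIL system is 4.0 with a standard deviation of 8.4", 173 subjects give 80% power against 2.2 with a two-sided one-sample t-test at 0.05, and 204 are enrolled to allow for about 15% attrition. Section 12.5 tests the primary endpoint against 2.2 degrees.

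No note says how each group's difference and SD were obtained, or why the last row departs from the pattern of the others.

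**The concern.** Two entries in the n=299 row stand out, and they differ in kind.

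- **Mean.** 22.0 minus 22.0 is 0.0, but 1.0 is printed and 299.0 goes into the weighted mean. At the printed precision this is a contradiction. The table handles equal means differently elsewhere: an n=9 row with 23.0 at both times prints 0.0.
- **SD.** 5.0 is far below what the rest of the table would suggest for component SDs of 14.1 and 10.3. This is an anomaly, not an impossibility.

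The row is nearly half the table, and the table is the only documented basis for the comparator. An error in the mean would misplace the benchmark. An error in the SD would misstate the planning variability. Either would change the power claimed for 173 subjects. The issue is separate from the step from 2.1 to 2.2 and from the method used to average the SDs. Settling those would leave this row as it is.

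**Working it through.** **Inputs.** Table rows and totals from section 12.2; true mean 4.0, SD 8.4, OPC 2.2, n = 173 and two-sided alpha 0.05 from section 12.3.

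**1. Reproducing the plan's figures.**
- Total n = 9 + 3 + 34 + 9 + 60 + 31 + 83 + 111 + 299 = 639. Weight of the last row = 299/639 = 46.8%.
- Weighted mean = 1326.8/639 = 2.08 (printed 2.1).
- Weighted SD = 5387.2/639 = 8.43 (printed 8.4).
- Power of the one-sample t-test (noncentral t, 172 df, noncentrality = (4.0 − OPC)/SD × √173): 1.8/8.4 × √173 = 2.82, power 80.0%. The plan's arithmetic is right for its inputs.
- 173/0.85 = 203.5, so 204 enrolled.

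**2. The mean.** Pre-op minus last follow-up equals the printed difference in eight of nine rows. Only n=299 fails (0.0 against 1.0).

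**3. The SD.** The implied correlation is r = (s₁² + s₂² − s_d²)/(2·s₁·s₂).
- n=299: (14.1² + 10.3² − 5.0²)/(2 × 14.1 × 10.3) = 0.964.
- n=111, same paper: (14.0² + 10.8² − 12.2²)/(2 × 14.0 × 10.8) = 0.54.
- n=83: (12.0² + 8.4² − 11.4²)/(2 × 12.0 × 8.4) = 0.42.
- The six paper 1 rows give 0.50 to 0.62. In each, the printed SD is the simple average of the two component SDs (for n=60, (13.0 + 9.6)/2 = 11.3), so these correlations follow from that rule and are not independent evidence.
- The smallest SD of change that 14.1 and 10.3 allow is 14.1 − 10.3 = 3.8 (at r = 1). So 5.0 is attainable.
- The averaging rule applied to this row would give (14.1 + 10.3)/2 = 12.2. Below, 12.2 is an assumption used to show sensitivity.

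**4. What the row does to the benchmark and SD.**
- Row difference set to 0.0: (1326.8 − 299)/639 = 1.61.
- Row SD set to 12.2: (5387.2 − 1495 + 299 × 12.2)/639 = 11.8.
- Row dropped: mean (1326.8 − 299)/340 = 3.02; SD (5387.2 − 1495)/340 = 11.4.

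**5. Power at n = 173, true mean 4.0.**

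| Resolution of the row | OPC | SD | Power |
|---|---|---|---|
| As printed | 2.2 | 8.4 | 80% |
| Mean corrected to 0.0 only | 1.61 | 8.4 | about 96% |
| SD taken as 12.2 only | 2.2 | 11.8 | 51% |
| Both | 1.61 | 11.8 | about 76% |
| Row dropped, OPC recomputed | 3.02 | 11.4 | about 20% |
| Row dropped, OPC left at 2.2 | 2.2 | 11.4 | 54% |

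Correcting the mean lowers the benchmark and raises power. Raising the SD lowers power.

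**The case against.** The strongest defence is that 1.0 and 5.0 were taken directly from the source as a reported mean change and its SD. The products 299.0 and 1495.0 fit that. All four means from this paper are whole degrees (29, 23, 22, 22). If they were rounded, a true change of about 0.5 to 1.0 could sit behind 22 and 22, and the weighted mean would then lie between (1027.8 + 149.5)/639 = 1.84 and 2.08. A mistyped pre-op or follow-up cell would also leave 1.0 correct. On the SD, this paper's other row does not follow the averaging rule (12.2 printed, average 12.4), and neither does the n=83 row (11.4 printed, average 10.2), so nothing establishes 12.2 as the replacement.

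All of this stands as a limit on what can be concluded. It does not dispose of the point. The plan gives no such explanation, and if it is the right one, the table mixes directly reported changes with averaged SDs and should say so.

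A reader might infer that the study is underpowered, at roughly 51% to 76%. The documents do not support that. Those figures need the 5.0 to be wrong, and they leave out the case where only the mean is corrected, in which power rises.

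It can also be said that the formal hypothesis in section 12.2 uses OPC − δ = 2.2 − 2 = 0.2. Against 0.2, power at n = 173 is about 99% even with SD 11.8. That is fair, but sections 12.3 and 12.5 both work against 2.2, and the 80% claim is made there. Which threshold governs is a separate question.

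**Conclusion.** The point holds as an unresolved inconsistency in an influential input. The n=299 row contradicts itself on the mean and is anomalous on the SD. It carries 47% of the weight behind the 2.1 (used as 2.2) and the 8.4, so the 80% power at n = 173 is not supported until the row is resolved. Depending on the resolution, power runs from about 20% to about 96%, and the benchmark from 1.61 to 3.02 degrees, against an assumed advantage of 1.8.

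These figures assume a true mean of 4.0, the plan's own weighting and SD-averaging method, and, where used, a row SD of 12.2. Which cell is wrong cannot be told from the documents.

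**What to change.** Re-extract the n=299 row from its cited source and record how its difference and SD of change were obtained. Correct whichever cell is wrong, or drop the row if it cannot be reconciled. Then recompute the OPC and the planning SD together, carry the OPC through sections 12.2, 12.3 and 12.5, and restate in section 12.3 the power that 173 evaluable subjects give at those values. No power figure should be set in advance, and the 1.8-degree difference should not be kept if the OPC moves.

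The cost is re-reading one paper and editing three sections. Enrolment does not change. The downside is that the stated power may become less favourable.

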5 STUDY OBJECTIVES/OUTCOMES

5.1 Primary Effectiveness Objective

The primary effectiveness objective is:

Restoration and maintenance of thoracic kyphosis and coronal curve correction.

- Quantitative assessment:
 - Cobb Angles – Coronal and Sagittal
 - Thoracic kyphosis as measured from the upper endplate of T4 to the lower endplate of T12
 - Lumbar lordosis as measured from the lower endplate of L1 to the upper endplate of S1

The increased stiffness of the MESA Rail is designed for the restoration and maintenance of thoracic kyphosis as well as coronal correction of deformities such as AIS after surgery. The restoration and subsequent maintenance of the thoracic kyphosis and coronal curve correction during surgery is expected to be as good as if not better than results reported for standard Ø5.5mm and Ø4.5mm CoCr pedicle screw and rod systems in these patient populations.

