6 STUDY ENDPOINT

The endpoint of this study is to determine that the restoration and/or maintenance of thoracic kyphosis and coronal curve correction is better than with similar CoCr systems.

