12.5 Analysis of Primary Endpoint

The primary effectiveness endpoint will be evaluated by a two-sided exact test of the MESA Rail implant success rate (mean thoracic correction) against the literature reported mean thoracic correction of 2.2 degrees.

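### No single primary decision rule: non-inferiority, superiority and a 0.2-degree boundary are all stated, while the sample size and the test use 2.2 degrees with no margin

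*Combined protocol and SAP*

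**What the plan says.** Five places describe the primary comparison, and they differ.

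- **Section 12.2, opening paragraph:** "The primary hypothesis of this trial is that the clinical performance of the K2M MESA Rail implant is non-inferior to the clinical performance achieved" with standard CoCr rods. The endpoint is a proportion: "The primary effectiveness endpoint is the rate of overall subject success (minimal loss of thoracic kyphosis) at 24 months".
- **Section 12.2, after the literature table:** "The study hypothesis is that the RAIL system is superior to other systems in Thoracic Kyphosis Correction". The formal statement that follows is H0: μ_R < OPC − δ against H1: μ_R ≥ OPC − δ, where μ_R is a mean, OPC = 2.2 and δ = 2 degrees.
- **Section 12.3:** 173 subjects give 80% power "to detect a statistically significant difference between the mean correction and the OPC of 2.2 using a two-sided one-sample t-test" at the 0.05 level, if the true mean is 4.0 and the SD 8.4. δ does not appear.
- **Section 12.5:** a two-sided exact test of a success rate, glossed in brackets as a mean, "against the literature reported mean thoracic correction of 2.2 degrees". δ does not appear here either.
- **Section 6:** the aim is to show that the result "is better than with similar CoCr systems".

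Section 5.1 adds the softer expectation that the result "is expected to be as good as if not better than results reported for standard" CoCr systems. No section orders these claims or gives a significance level for a test that uses the margin.

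**The concern.** Non-inferiority with a 2-degree margin and superiority with none are different claims with different pass marks. Section 12.2 places the superiority sentence directly above hypotheses that, if larger values are better, have the non-inferiority form. Rejecting that H0 does not show superiority over 2.2, yet the text would let it be reported so. Section 12.5 does name a comparison value, but nothing says that it overrides the formal hypotheses in 12.2. The governing rule could therefore be settled after the data are seen.

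Two further conflicts decide what the written hypotheses mean.

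- **Sign.** The table in 12.2 takes preoperative minus last follow-up (first row 31.9 − 26.0 = 5.9), so a positive value is loss of kyphosis. The hypotheses call the quantity correction and put large values in H1.
- **Endpoint.** It is a rate in the opening of 12.2, a mean in the hypotheses and in 12.3, and both at once in 12.5.

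**Working it through.** **Inputs.** OPC 2.2 and δ 2 (section 12.2). Planning mean 4.0, SD 8.4, 173 evaluable, 204 enrolled, two-sided 0.05, 80% power, about 15% attrition (section 12.3). The level for the written H0 is not stated; I use one-sided 0.025, the counterpart of two-sided 0.05, and show one-sided 0.05 as a range. All powers are one-sample t-test powers from the noncentral t distribution with n − 1 degrees of freedom and noncentrality (true mean − boundary)/(SD/√n).

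**1. The plan's own figure.** SE = 8.4/√173 = 0.6386. Noncentrality = (4.0 − 2.2)/0.6386 = 2.82. Two-sided power at 0.05 is 80.03%; with 172 subjects it is 79.8%. So 173 is right, and 173/0.85 = 203.5, giving 204. The figure belongs to the test against 2.2 with no margin. It does not power the written H0 and H1.

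**2. Pass marks if larger is better.** The written boundary is 2.2 − 2 = 0.2. The mark is boundary + t × SE.

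| n | Superiority over 2.2, two-sided 0.05 | Written H0, one-sided 0.025 | Written H0, one-sided 0.05 |
|---|---|---|---|
| 173 | 2.2 + 1.974 × 0.6386 = 3.46 | 0.2 + 1.26 = 1.46 | 0.2 + 1.06 = 1.26 |
| 204 (SE 0.588) | 2.2 + 1.16 = 3.36 | 0.2 + 1.16 = 1.36 | – |

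With 173 subjects, an observed mean between 1.46 and 3.46 succeeds under one rule and fails under the other.

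**3. A device exactly equal to the benchmark (true mean 2.2).** Noncentrality against 0.2 is 2/0.6386 = 3.13.

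- Rejects the written H0: 87.6% (n = 173, one-sided 0.025), 93.0% (n = 173, one-sided 0.05), 92.3% (n = 204, one-sided 0.025).
- Shows superiority over 2.2: 2.5%.

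**4. The table's sign, where positive is loss.** The written H1 (mean at or above 0.2) then favours loss. With n = 173 and one-sided 0.025:

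- a true mean loss of 4.2 degrees, 2 more than the benchmark, rejects H0 more than 99.9% of the time;
- zero loss rejects H0 1.2% of the time (2.5% at one-sided 0.05).

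On this sign the planning mean of 4.0 is also worse than 2.2. The favourable value at the same distance is 2.2 − 1.8 = 0.4 degrees of loss, and 173 still holds by symmetry.

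**5. The margin.** δ/OPC = 2/2.2 = 0.91, and the documents give no justification for it. Non-inferiority power at true equality, one-sided 0.025, SD 8.4:

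| Margin (degrees) | Power at n = 173 | Evaluable n for 80% |
|---|---|---|
| 2.0 | 88% | 141 |
| 1.8 | 80% | 173 |
| 1.5 | 65% | 249 |
| 1.1 (half the benchmark) | 40% | 460 |

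**The case against.** The best defence is that 12.3 and 12.5 are the operative sections, that both compare with 2.2 two-sided and without a margin, and that 12.5 is the section on the primary analysis. If only that comparison were applied, an equal device would be found superior 2.5% of the time, as intended. The 88% arises only if the written H0 is tested and the result is called superiority. This is correct, and it is why the risk is conditional.

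It does not remove the conflict. Nothing gives 12.5 precedence over the formal hypotheses. Reading 12.5 as governing leaves the non-inferiority hypothesis with no test and δ with no use. Section 12.5 is also unclear in itself: it names an exact test of a rate where 12.3 names a t-test of a mean.

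Two smaller points stand. Sections 5.1 and 6 are statements of expectation and aim, so the contradiction rests on 12.2, 12.3 and 12.5. And 2.2 is itself unreconciled: the table in 12.2 shows a weighted mean of 2.1 (its own products sum to 1326.8, and 1326.8/639 = 2.08). The absolute pass marks and the 91% ratio inherit that; the powers by margin do not.

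**Conclusion.** The concern holds and must be fixed before analysis. The hypotheses, the sample size and the planned test do not describe one decision rule, and the two candidate pass marks lie 2 degrees apart (1.46 and 3.46 at n = 173). A device no better than the benchmark could be reported as superior with probability 88% if the written H0 is used under its superiority label, against 2.5% under the test that was sized. These figures assume SD 8.4, a benchmark of 2.2, larger values better, and one-sided 0.025 for the written H0. On the table's loss sign the written rule runs backwards. The 173/204 arithmetic is sound for a mean endpoint tested against 2.2; confidence in the contradiction is high.

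**What to change.** 1. **Sign and endpoint.** State the sign, and state that the quantity tested is the mean change in thoracic kyphosis at 24 months. Replace the rate wording in 12.2 and 12.5, and replace the exact test in 12.5 with the one-sample t-test of 12.3. If the chosen sign is loss, restate the 4.0 planning mean on the favourable side. If the rate is kept as primary, none of these power figures apply and the sample size must be redone.

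2. **One rule.** Make H0/H1, test, sample size and claim agree by one of two routes.
   - *Route 1:* a single superiority test of the mean against the benchmark, two-sided 0.05, 80% power for a 1.8-degree difference with 173 evaluable. Delete δ and the non-inferiority statement.
   - *Route 2:* a fixed sequence. First non-inferiority at one-sided 0.025, with a justified margin on the unfavourable side; then superiority against the benchmark at two-sided 0.05, only if the first step is met. State the non-inferiority power at true equality for the chosen margin.

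3. **Claim wording.** Under either route, do not call a result superior or better if it only clears a boundary that contains δ. Align sections 5.1 and 6.

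4. **Alongside.** Reconcile 2.2 with the table's 2.1. Say whether coronal correction, which the synopsis and sections 5.1 and 6 include but sections 12.2 to 12.5 do not test, is part of the primary claim.

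**Cost.** With the mean as endpoint, Route 1 changes wording only and keeps 173/204. So does Route 2 if the justified margin is at least 1.8 degrees. A margin of 1.5 needs 249 evaluable for 80% power at true equality, or 249/0.85 = 293 enrolled. The price in either case is that a result showing only non-inferiority cannot be called superior.
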